7.5.2 Overall Survival

OS is defined as the time in months from the first day of study drug administration (Day 1) to death. Subjects who are alive at the end of study will be censored at the date of last contact. OS primary analysis includes all follow-up data, including follow-up data in the retreatment period or after the start of subsequent anti-cancer therapy. Date of death will be obtained from the AE CRF page, or End of Study CRF page, or the Survival Status CRF page.

Censoring of OS will be performed as detailed in [Table 2](#).

Table 2 – Overall Survival Censoring Methodology

Situation	Date of Death or Censoring	Outcome*
Death	Date of death	Event
No documented death	Date last known alive	Censored

*Time (month) = (Date of Death or Censoring – Date of first study drug administration + 1)/ 30.44

OS will be estimated using the Kaplan-Meier method. In addition to the range, the median OS and its 2-sided 95% confidence interval using the method by Klein and Moeschberger; 1997) with complementary log-log transformation will be produced. Additionally, proportion of subjects alive at 6, 9 and 12 months from the initiation of study treatment using the Kaplan-Meier method and corresponding 2-sided 95% confidence intervals using complementary log-log transformation will be estimated.

7.5.3 Sensitivity and Subgroup Analysis

Subgroup analyses of ORR and OS will include all subgroups defined in Section 5.3.

Additional sensitivity analyses may be performed if deemed appropriate.

7.6 Analysis of Secondary Efficacy Endpoints

All secondary efficacy analyses will be summarized for the efficacy analysis populations defined in Section 5.

7.6.1 Duration of Response

Duration of objective response is defined as the time in months from the initial CR or PR to the time of disease progression or death on study, whichever occurs first during the initial treatment period. Only subjects with a confirmed response of CR or PR will be included.

For subjects who are alive and have not experienced disease progression on the study, duration of objective response will be censored at the day of the last tumor assessment during the initial treatment period. If no tumor assessment after the initial response is available, then the duration of response will be one day. Censoring rules for duration of response will be performed as detailed in [Table 3](#). If multiple visits exist, the latest

evaluable assessment date will be used for censoring except for PD, which will use the earliest assessment date when PD was recorded. Symptomatic deterioration will not be considered PD since a lesion assessment will need to be performed to verify disease progression. If there are multiple scans with multiple dates provided for a visit, the lesion assessment date will be the last scan date recorded for that visit to define baseline and the earliest scan date within the visit to determine the lesion assessment date post-baseline.

Table 3 - Duration of Response Censoring Methodology

Situation	Date of Progression/Death or Censoring	Outcome*
Death or disease progression per RECIST 1.1 at any time during initial treatment period	Date of death or first disease assessment showing disease progression, whichever occurs first	Event
Progression caused by new lesion during initial treatment period	Date new lesion is detected	Event
Progression caused by worsening of non-target lesion(s) or target lesion(s) during initial treatment period	First assessment date documenting the increase in target lesion(s) meeting criteria for progression, or the worsening non-target lesion(s)	Event
Progression caused by multiple causes (e.g. new lesions and worsening of non-target lesions) during initial treatment period	First date among the multiple sources of PD	Event
Subsequent anti-cancer treatment started before death or without documentation of disease progression beforehand	Date of last evaluable disease assessment prior to start of subsequent anti-cancer treatment	Censored
Death or disease progression after missing two or more consecutively scheduled disease assessments during initial treatment period	Date of last evaluable disease assessment visit without documentation of disease progression that is before the missed visit	Censored
Alive and without documentation of disease	Date of last evaluable	Censored

progression during initial treatment period	disease assessment during initial treatment period	
---------------------------------------------	----------------------------------------------------	--

*Time (month) = (Date of Progression/Death or Censoring – Date of first response (CR or PR) + 1)/ 30.44.

For Duration of Objective Response, only subjects with a confirmed response of CR or PR will be included.

Duration of objective response will be estimated using the Kaplan-Meier method. The median duration of objective response and the corresponding 2-sided 95% confidence interval will be produced in addition to the range. The proportion of responders who have not yet experienced disease progression or death at 6, 9, and 12 months from the start date of CR or PR will be summarized descriptively based on Kaplan-Meier estimates. The estimates will be accompanied by a two-sided 95% CI.

Duration of best overall response will also be summarized. This analysis will include subjects with a response of CR or PR, regardless of confirmation.

Duration of objective response and duration of best overall response will be summarized based on IRC assessments, as well as investigator assessments.

7.6.2 Clinical Benefit Rate

Clinical Benefit is defined as the achievement within a subject of a Best Overall Response of CR, PR or SD with SD of a minimum duration of 42 days (-7 days to allow for scheduled visit window per the protocol) from the first dose date, prior to receiving any subsequent anticancer therapy and retreatment; as defined by RECIST version 1.1. CBR is defined as the proportion of subjects with clinical benefit. CBR will be presented as a number and percentage with two-sided exact 95% binomial confidence interval (CI). CBR will be summarized based on IRC assessments, and based on investigator assessments, respectively.

7.6.3 Duration of Clinical Benefit

DOCB [CR, PR, or SD with SD of a minimum duration of 42 days (-7 days to allow for scheduled visit window per the protocol from the first dose date)] is defined as time in months from the initial CR, PR, or SD to the time of disease progression or death on

study, whichever occurs first during the initial treatment period. Only subjects with the response of CR, PR, or SD are included.

For subjects who are alive and have not experienced disease progression on the study, DOCB will be censored at the day of the last tumor assessment during the initial treatment period. Censoring rules for duration of clinical benefit will be performed as detailed in Table 3 above. If multiple visits exist, the latest evaluable assessment date will be used for censoring except for PD, which will use the earliest assessment date when PD was recorded. Symptomatic deterioration will not be considered PD since a lesion assessment will need to be performed to verify disease progression.

DOCB will be estimated using the Kaplan-Meier method. The median duration of clinical benefit and the corresponding 2-sided 95% confidence interval will be produced in addition to the range.

Calculation of DOCB will be based on IRC assessments, as well as investigator assessments.

7.6.4 Progression-Free Survival

PFS is defined as the time in months from the first day of study drug administration (Day 1) to disease progression or death on study, whichever occurs first during the initial treatment period.

For subjects who are alive and have not experienced disease progression during the initial treatment period, PFS will be censored on the day of the last tumor assessment during the initial treatment. Subjects with no post-baseline response assessment PFS will be censored and have a PFS duration of one day. Censoring rules for PFS will be performed as detailed in Table 4 below. If multiple dates exist for a given visit, the latest evaluable assessment date will be used for censoring except for PD, which will use the earliest assessment date when PD was recorded. Symptomatic deterioration will not be considered PD since a lesion assessment will need to be performed to verify disease progression.

Table 4 – Progression-Free Survival Censoring Methodology

Situation	Date of Progression/Death or Censoring	Outcome*
Death or disease progression per RECIST 1.1 at any time during initial treatment period	Date of death or first disease assessment showing disease progression, whichever occurs first	Event
Death before first planned disease assessment	Date of death	Event
Progression caused by new lesion during initial treatment period	Date new lesion is detected	Event
Progression caused by worsening of non-target lesion(s) or target lesion(s) during initial treatment period	First assessment date documenting the increase in target lesion(s) meeting criteria for progression, or the worsening non-target lesion(s)	Event
Progression caused by multiple causes (e.g. new lesions and worsening of non-target lesions) during initial treatment period	First date among the multiple sources of PD	Event
Subsequent anti-cancer treatment started before death or without documented disease progression	Date of last evaluable disease assessment prior to start of non-protocol anticancer treatment	Censored
Death or disease progression after missing two or more consecutively scheduled disease assessments during initial treatment period	Date of last evaluable disease assessment visit without documentation of disease progression that is before the missed visit	Censored
Alive and without documentation of disease progression during initial treatment period	Date of last evaluable disease assessment during initial treatment period	Censored

*Time (month) = (Date of Progression/Death or Censoring – Date of first dose + 1) / 30.44

PFS will be estimated using the Kaplan-Meier method. The median duration of PFS and the corresponding 2-sided 95% confidence interval will be produced in addition to the range.

Proportion of subjects alive and without PD at 6, 9 and 12months from the initiation of study treatment will be summarized based on Kaplan-Meier estimates, with the corresponding 2-sided 95% confidence intervals.

7.6.5. Subgroup Analysis of Secondary Endpoints

Subgroup analyses of secondary endpoints of DOR, CBR, DOCB and PFS may include the subgroups described in Section 5.3. For example, DOR may be analyzed in the DLL3 subgroups defined in Section 5.3 by current line of therapy (3L vs 3L+), if there are sufficient number of responders in each subgroup. Subgroup analysis of PFS by DLL3 subgroups will be performed by current line of therapy (3L vs 3L+).

Additional analysis of the secondary endpoints in the modified ITT population, regardless of the DLL3 score, will be included.

7.7 Analysis of Safety Endpoints

Unless otherwise stated, all safety analyses will be carried out in the safety analysis population by initial treatment period and retreatment period. No formal statistical inference or missing data imputations are planned.

and for all dosed subjects combined regardless of the DLL3 score.

7.7.1 Treatment Emergent Adverse Events

All adverse events will be coded using the MedDRA dictionary. Safety analyses will involve examination of the incidence, severity, and type of treatment-emergent adverse events (TEAE) and serious adverse events as reported by the investigators. A treatment-emergent adverse event (TEAE)/treatment emergent serious adverse event is defined in Section 6. An applicable AE/SAE is considered ‘related’ if its relationship to study drug was judged by the investigator. Ongoing adverse events that have a change in severity, action taken with study drug, or outcome will be recorded multiple times with the

changes. If a subject has multiple occurrences of an adverse event with the same system organ class, the most severe event will be chosen. Similarly, if a subject has multiple occurrences of an adverse event with the same preferred term, the most severe event will be chosen. If a partial date does not provide enough information to determine the onset date relative to first dosing date, then the adverse event will be assumed as treatment-emergent, otherwise partial dates will be imputed relative to the first dose date. TEAEs will be summarized by system organ class and preferred term. These summaries will be presented by system organ class and preferred term for the following subsets:

- All TEAEs (All grades, and for maximum grade of 3 or 4)
- All TESAEs (All grades, and for maximum grade of 3 or 4)
- All TEAEs leading to study drug discontinuation (All grades, and for maximum grade of 3 or 4)
- All TEAEs leading to death

All drug-related TEAEs, and all drug-related TESAEs will also be summarized. The above tables will also be categorized by gender and age group (<65, \geq 65 years). For tables classifying TEAEs by severity, if a subject has multiple occurrences of an adverse event with the same system organ class, the most severe event will be chosen. Similarly, if a subject has multiple occurrences of an adverse event with the same preferred term, the most severe event will be chosen.

Adverse events of special interest (AESI) identified by the specific search criteria outlined in Appendix F will be summarized by System Organ Class (SOC) and Preferred Term (PT) [REDACTED]

Tabulation of TEAEs will be based on subjects in safety analysis population. The number and percent of subjects with an adverse event will be displayed. In general, the denominator for the percent of subjects with an adverse will be the number of subjects in the safety analysis population or the number of subjects in safety analysis population within a subgroup if a subgroup is summarized.

All deaths that occur on study will be reported in a subject listing, which will include the primary cause of death and the number of days between the date of the last dose of study drug and death.

TEAE that occurred during retreatment period will be summarized separately for those who receive retreatment, provided there is sufficient number of subjects who received retreatment; otherwise listings will be provided. Adverse events that occurred after the start of subsequent anti-cancer therapy, if not included in the retreatment period, will be summarized separately by system organ class and preferred term, provided there is sufficient number of subjects; otherwise listings will be provided. Adverse events with onset prior to first dose date will be considered pre-treatment. All pre-treatment adverse events will be summarized by system organ class and preferred term, provided there is sufficient number of subjects; otherwise listings will be provided for pre-treatment adverse events. Listing of all AEs, SAEs, AEs leading to study drug discontinuation, and death will be reported.

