9.2.9.1 Treatment Emergent Adverse Events

Adverse events will be defined as treatment emergent if they are newly occurring or worsen following study treatment. The incidence of treatment-emergent adverse events and treatment-related adverse events will be tabulated. Adverse events will be classified by system organ class and preferred term using the Medical Dictionary for Regulatory Activities (MedDRA).

AEs will be listed and summarized by MedDRA preferred term, severity, and relationship to study drug. In the event of multiple occurrences of the same AE with the same preferred term in one subject, the AE will be counted once as the occurrence, using the event with highest severity grade and strongest causal relationship. The incidence of AEs will be tabulated by preferred term.

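### The high-grade adverse event rows stop at maximum Grade 4, so a subject whose worst event is fatal drops out of them; the gap is real mainly for discontinuations and the gender and age splits

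*SAP*

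**What the plan says.** SAP 7.7.1 (Treatment Emergent Adverse Events) sets two rules.

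- **Counting.** Within an SOC, "If a subject has multiple occurrences of an adverse event with the same system organ class, the most severe event will be chosen". Within a PT, "if a subject has multiple occurrences of an adverse event with the same preferred term, the most severe event will be chosen". Protocol 9.2.9.1 has a matching rule per preferred term, "using the event with highest severity grade and strongest causal relationship".
- **Grade limit.** Three summaries by SOC and PT carry the same limit. The first bullet, for every event, begins "All TEAEs (All grades, and for maximum grade of 3 or 4". The second bullet repeats the limit for serious events. The third, for events that ended treatment, begins "All TEAEs leading to study drug discontinuation (All grades, and for maximum grade of 3 or 4". A fourth summary covers TEAEs leading to death.

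The section also has an ongoing event recorded again whenever it changes (the rule begins "Ongoing adverse events that have a change in severity, action taken with study drug, or outcome will be recorded multiple times with the"). An event that worsens therefore leaves several records with different grades.

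The protocol adopts CTCAE v4.03 for severity (7.6.1.1 and 7.7). It requires the event that caused a death to be recorded on the CRF as well as the SAE form (7.6.1.2). Neither document specifies an adverse event summary for Grade 3 or higher.

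**The concern.** Each rule is ordinary alone, but together they have a side effect. Taking the maximum first and then keeping only maxima of 3 or 4 removes a subject whose maximum is 5. The earlier Grade 3 or 4 record of the same event has already been discarded, so nothing puts the subject back in that row.

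The effect runs one way. Read as a measure of high-grade toxicity, the row can only be too low, and it is lowest relative to the truth for the terms that kill most often. Fatal TEAEs are foreseeable: Protocol 1.1.1 describes recurrent disease as rapidly fatal. The limit also differs from the open-ended cuts used elsewhere: SAP 7.7.2 lists laboratory values from Grade 3 upward, and several entries in Protocol Table 5-2 are worded as a grade or higher.

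**Working it through.** The plan states no figure that depends on this rule, so there is none to reproduce. The check applies the rule to a small invented data set, then asks which planned outputs recover the missing count.

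**Step 1: the rule on four invented subjects, all with events in one SOC.**

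| Subject | Records | Maximum in SOC | In the 3-or-4 row? | In a 3-or-higher row? |
|---|---|---|---|---|
| A | one PT, Grade 3 becoming Grade 5 | 5 | no | yes |
| B | one PT at Grade 4, another PT at Grade 5 | 5 | no | yes |
| C | Grade 3 | 3 | yes | yes |
| D | Grade 2 | 2 | no | no |

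The SOC row counts 1 subject under the SAP rule and 3 under Grade 3 or higher. At PT level, A's term counts 0 against 1, and B's fatal term counts 0 against 1. B's separate Grade 4 term is counted in its own PT row under both rules. The loss is therefore confined to the PT with the fatal event and to its SOC.

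**Step 2: size.** With f affected subjects among N treated, the row falls by f/N. The documents give neither f nor the final N, so both are assumed. N = 123 is the DLL3-high third-line target and hence a low value for the treated total; N = 200 is a larger illustration.

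| f | f/123 | f/200 |
|---|---|---|
| 1 | 0.8 points | 0.5 points |
| 3 | 2.4 points | 1.5 points |
| 6 | 4.9 points | 3.0 points |
| 12 | 9.8 points | 6.0 points |

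**Step 3: what the planned outputs recover.** These are the titles in SAP Appendix G.

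| Summary | By-grade table | Leading-to-death table | Grade 3-or-higher count recoverable? |
|---|---|---|---|
| TEAEs | 14.3_1.2.3 | 14.3_2.4.1 | yes |
| Drug-related TEAEs | 14.3_1.3.2 | none of its own | yes, from the by-grade table |
| Serious TEAEs | 14.3_2.1.2 | none of its own | yes, from the by-grade table |
| Drug-related serious TEAEs | 14.3_2.2.2 | none of its own | yes, from the by-grade table |
| TEAEs leading to discontinuation (14.3_2.3.1) | none | none of its own | not from the planned tables |
| TEAEs by gender | none | 14.3_2.8.6 | only by adding the two tables |
| TEAEs by age group | none | 14.3_2.9.6 | only by adding the two tables |

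In a by-grade table each subject sits at one maximum grade per PT and SOC, so Grades 3, 4 and 5 add up without double counting, provided the table shows Grade 5. For discontinuations, the general leading-to-death table does not help, because it does not separate the fatal events that also led to discontinuation.

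**The case against.** The strongest reply is that nothing is hidden or mislabelled. The row is called maximum Grade 3 or 4 and reports exactly that; the SAP never presents it as a Grade 3-or-higher rate. Fatal events have their own table by SOC and PT on the same safety population, and they remain in every all-grades row, in the deaths listing and in four by-grade tables. If fatal means Grade 5, the two rows are mutually exclusive and can be added. With assumed counts of 20 subjects at maximum Grade 3 or 4 and 8 at Grade 5 among 200, the row shows 20/200 = 10%, the death table shows 8/200 = 4%, and the sum is 28/200 = 14%. Safety analysis is descriptive (SAP 7.7), and no test or stated stopping rule uses the row.

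Most of this stands. A reader might infer that the plan conceals lethal toxicity, or that a separate fatal-event table cannot make good the high-grade count. The documents support neither: for the main TEAE and serious TEAE displays the count is recoverable. A reader might also point to the effusions that the protocol calls potentially life-threatening. In Protocol Appendix 12.5, life-threatening pericardial and pleural effusions are Grade 4, so they are in the row unless fatal.

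The reply does not cover discontinuations, where there is no by-grade table and no matching death table. It also relies on the death table holding exactly the Grade 5 subjects, which the SAP does not say.

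A further objection is that the documents never mention Grade 5. The Appendix 12.5 excerpt ends at Grade 4, and Protocol 7.6.1.2 treats death as an outcome, recorded separately from grade. If a site left a fatal event at Grade 4 with outcome death, the subject would stay in the row. That makes the point conditional, and it is itself a reason to write the convention down.

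**Conclusion.** The point holds as a minor defect of presentation. As written, and if fatal events are graded 5 under the adopted CTCAE version, the high-grade rows omit any subject whose worst event in that PT or SOC was fatal. The bias has a fixed direction and a size of 1/N per affected subject: 0.8 percentage points at an assumed N of 123, less at a larger N. The total cannot be estimated, because the documents give no number of fatal TEAEs and do not say how many would also be coded as leading to discontinuation.

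The practical gap is limited to TEAEs leading to discontinuation, where the planned tables do not yield a Grade 3-or-higher count, and to the gender and age splits, where it has to be pieced together from two tables. No efficacy result or formal inference is affected.

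**What to change.** In the three bullets of SAP 7.7.1, replace the limit of maximum Grade 3 or 4 with maximum Grade 3 or higher. Alternatively, show Grades 3, 4 and 5 as separate columns with a Grade 3-or-higher total. Apply the same display to the discontinuation table and to the gender and age splits. Add one sentence stating that an event with a fatal outcome is graded 5, and keep the separate table of TEAEs leading to death.

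The cost is one SAP edit and the matching table shells, with no new data. The only downside is that reported high-grade rates will be slightly higher where fatal events occur.
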